### **3.2 Analysis Populations**

There will be four analysis populations for this study:

The Intent-to-treat (ITT) Population will include all participants who are randomized. Participant disposition and baseline demographics will be summarized by IP group (Group 1, 2, and 3) and overall for the ITT population according to the group which the participant is randomized to.

The Safety Population will include all randomized participants who receive at least one dose of either antibiotic or AV7909. Participants will be included in the IP group (Group 1, 2, and 3) according to the treatment they received.

The PK Population will include all participants in Group 1A and Group 2A who:

- Received two doses of AV7909 according to the protocol (e.g., correct dose, no temperature excursion, and within the study-specified windows).
- If in Group 1A, received at least 5 of the 7 in-clinic ciprofloxacin doses between Day 4 through the morning of Day 8 and between Day 31 through the morning of Day

35; or if in Group 2A, received at least 7 of the 9 in-clinic doxycycline doses between Day 2 through the morning of Day 8 and between Day 32 through the morning of Day 38.

- Have adequate data for calculation of the PK parameters ( $AUC_{0-12h}$  and  $C_{max}$ ) at the Day 8 (both Group 1A and 2A) and Day 35 (Group 1A) or Day 38 (Group 2A) visits.
- Have no protocol deviations/events that would affect ciprofloxacin or doxycycline steady state PK assessment or immunogenicity results.

Exclusion of participants from population will be done on a case-by-case basis at the time of the PK parameter analysis.

The PK Population will be used for all PK analyses. Participants will be included in the treatment group (Group 1A or Group 2A) according to the antibiotic received.

The Immunogenicity Population will include all randomized participants who:

- Received two doses of AV7909 according to the protocol (e.g., correct dose, no temperature excursion, and within the study-specified windows).
- Had a valid immunogenicity (TNA) result at Day 1 (pre-vaccination) with no evidence of previous exposure to anthrax or an anthrax vaccine (i.e., TNA below the limit of detection of 0.059).
- Had a valid immunogenicity (TNA) result at Day 37, within the study-specified window.
- Participants in Group 1 or Group 2 should have taken at least 50% of the protocol-specified antibiotic doses.

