## 6.5 PK Analyses

All PK analyses will be conducted based on the PK Population. All PK data listings will be presented based on the Safety Population.

PK concentration data will be summarized by study day and nominal time. The trough concentrations will be summarized by study day. The summary statistics for concentration data will include n, arithmetic mean, SD, median, minimum, maximum, and coefficient of variation (CV%).

PK parameters in **Table 3** will be summarized by study day. Summary of  $t_{max}$  will include n, median, minimum, and maximum only. For other PK parameters, n, arithmetic mean, SD, median, minimum, maximum, coefficient of variation (CV%), geometric mean, and geometric CV% will be presented.

The CV% is computed as:

$$CV\% = 100 \times (SD/Mean).$$

The geometric mean is computed as:

$$\text{Geometric mean} = \exp(\text{arithmetic mean of log transformed data}).$$

The geometric CV% is computed as:

$$CV\% \text{ geometric mean} = (\text{sqrt}(\exp(\text{variance for log transformed data}) - 1)) \times 100.$$

Individual as well as arithmetic mean concentration-time profile plots for serum concentration and trough concentrations will be presented in linear and semi-logarithmic scale.

The scatter plots of individual and geometric mean values for  $AUC_{0-12h}$  and  $C_{max}$  for ciprofloxacin and doxycycline will be presented for single dose and steady state profiles. The scatter plots of individual and geometric mean values for the ratio of  $AUC_{0-12h}$  and  $C_{max}$  will be presented for single dose and steady state profiles.

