### 6.5.2 Equivalence Testing for Secondary PK Endpoints

For each antibiotic, the secondary PK analyses will be performed to evaluate the effect of vaccination with AV7909 on the single-dose PK profile. The equivalence tests will be conducted in the similar statistical manner as the primary analyses. If the 90% CIs for geometric mean of the within-participant ratios of the single-dose values of  $AUC_{0-12h}$  and  $C_{max}$  post two doses of AV7909 (Day 31 for ciprofloxacin and Day 32 for doxycycline) vs. pre-vaccination of AV7909 (Day 4 for ciprofloxacin and Day 2 for doxycycline) fall entirely within the equivalence range of [0.80, 1.25] for both  $AUC_{0-12h}$  and  $C_{max}$ , it is concluded that AV7909 vaccine has no effect on the single-dose PK for ciprofloxacin or doxycycline.

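### The single-dose PK comparisons use a population defined by steady-state criteria, so valid single-dose pairs can be left out for reasons that do not bear on them

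*SAP*

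**What the plan says.** SAP 3.2 defines one PK Population and states: "The PK Population will be used for all PK analyses". SAP 6.5 repeats the rule: "All PK analyses will be conducted based on the PK Population". Protocol 10.3 gives the same instruction.

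Apart from two AV7909 doses given per protocol, the entry criteria in SAP 3.2 are:

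- **Dose count.** Group 1A must have "received at least 5 of the 7 in-clinic ciprofloxacin doses between Day 4 through the morning of Day 8 and between Day 31" and the morning of Day 35. Group 2A must have "received at least 7 of the 9 in-clinic doxycycline doses between Day 2 through the morning of Day 8", and likewise from Day 32 to the morning of Day 38.
- **Data.** AUC0-12h and Cmax must be calculable "at the Day 8 (both Group 1A and 2A) and Day 35 (Group 1A) or Day 38 (Group 2A) visits". Days 4, 31, 2 and 32 are not mentioned.
- **Deviations.** "Have no protocol deviations/events that would affect ciprofloxacin or doxycycline steady state PK assessment or immunogenicity results". Protocol 10.3 words this more broadly, as deviations affecting the PK of either antibiotic, and does not mention immunogenicity.
- **Discretion.** "Exclusion of participants from population will be done on a case-by-case basis at the time of the PK parameter analysis".

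SAP 6.5.2 then says that, for each antibiotic, "the secondary PK analyses will be performed to evaluate the effect of vaccination with AV7909 on the single-dose PK profile". It compares Day 31 with Day 4 for ciprofloxacin and Day 32 with Day 2 for doxycycline. SAP 2.3.2.2 describes these endpoints as informational with no hypothesis testing. SAP 6.5.2 nevertheless words a no-effect conclusion if both 90% intervals lie within 0.80–1.25.

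**The concern.** The single-dose profiles follow the opening dose of each antibiotic course. Under Protocol 8.1.2.2, 8.1.2.9, 8.1.4.2 and 8.1.4.9 the evening dose is given only after the 12-hour sample. Later doses in the course, and the Day 8 and Day 35 or 38 sessions, therefore cannot change those profiles.

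The population still requires them. Someone with complete Day 4 and Day 31 profiles and an inadequate Day 35 profile would leave the single-dose interval, the parameter summaries and the concentration summaries. The mismatch also runs the other way: membership does not require usable data on either single-dose day.

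At stake is precision on a secondary endpoint from which SAP 6.5.2 still draws a written conclusion.

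**Working it through.** **1. Which criteria bear on the single-dose pair?**

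| PK Population criterion | Bears on Day 31/4 or Day 32/2? |
|---|---|
| Two AV7909 doses per protocol | Yes: the comparison is before against after two doses |
| Adequate Day 8 and Day 35/38 AUC0-12h and Cmax | No |
| At least 5 of 7, or 7 of 9, in-clinic doses in each course | Only through the opening dose |
| No deviation affecting steady state or immunogenicity | Only if it also touches a single-dose profile |

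The dose-count criterion has a tolerance: 7 − 5 = 2 and 9 − 7 = 2. Exclusion on this ground needs three or more missed in-clinic doses in one course. Doses taken at home are not counted.

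**2. The plan's own sample size.** Inputs, from the protocol synopsis and SAP 2.4: CV of the within-participant ratio 30%, true ratio 0.95, limits 0.80–1.25, paired TOST at 5% per side.

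- SD of the log ratio: s = √ln(1 + 0.30²) = √ln 1.09 = 0.2936.
- Power is the probability that ln 0.80 + t·SE < estimate < ln 1.25 − t·SE, where t is the 95th percentile on n − 1 degrees of freedom and SE is the estimated standard error, integrated over the chi-square distribution of the variance.
- Result: 90.5% at n = 27 (the smallest n reaching 90%) and 95.5% at n = 34 (the smallest reaching 95%). Both stated figures reproduce.
- Allowance: 27 / 0.70 = 38.6, so 39. With 40 enrolled, 40 × 0.70 = 28 remain.

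**3. Carrying this to the single-dose ratio.** The documents give no CV or target n for it. I assume the same 30% CV and true ratio of 0.95. The half-width of the 90% interval on the log scale is t × 0.2936 / √n.

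| Pairs | Half-width (log) | Interval at 0.95 | Power, one parameter |
|---|---|---|---|
| 28 | 0.0945 | 0.864–1.044 | 91.4% |
| 34 | 0.0852 | 0.872–1.034 | 95.5% |
| 40 | 0.0782 | 0.879–1.027 | 97.7% |

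From 28 to 40 pairs the interval narrows by (0.0945 − 0.0782) / 0.0945 = 17%. That is a ceiling: it needs the whole 30% allowance to be used and all 12 excluded participants to have two valid single-dose profiles. If none of them has, the gain is zero.

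**4. Do other rules bring the pairs back?** No. The case-by-case sentence governs exclusion from the one population and gives no rule for retaining a single-dose pair. The SAP 6.4 rule on pre-dose values above 5% of Cmax is specific to single-dose days, but it only removes profiles. SAP 6.2 likewise only excludes.

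**The case against.** The strongest reply is that little is lost. The endpoint is informational, 28 pairs would still give about 91% per parameter under the assumed CV, and a common set keeps single-dose and steady-state results on the same people. All of that stands, and it limits the importance of the point.

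Few losses may be recoverable. Anyone who withdraws before Day 31 or 32, or fails the vaccination criterion, is lost under any sensible definition. The Day 8 session falls on the day of the first vaccination, and SAP 3.4 gives that day no window, so a participant absent on Day 8 would normally fail the vaccination criterion too. What remains is mainly:

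- an inadequate steady-state profile;
- failure in the 4 days (ciprofloxacin) or 6 days (doxycycline) after the second single-dose session;
- three or more missed in-clinic doses in a course;
- a deviation confined to steady state or immunogenicity.

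A reader might also infer three stronger points that the documents do not support:

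- **That any missed run-in dose excludes a participant.** Two missed in-clinic doses per course are tolerated.
- **That the data are discarded.** PK listings use the Safety Population (SAP 6.5), and exclusions are listed with reasons (SAP 5.1).
- **That restricting to those who completed steady-state sessions biases the single-dose ratio.** Nothing in the documents links completing Day 35 or 38 to a within-participant Day 31/4 or Day 32/2 ratio.

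The reply does not show that the steady-state criteria are needed for the single-dose comparison. The common-denominator argument is also weaker than it looks, because the SAP 6.4 pre-dose rule already lets the denominators differ.

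**Conclusion.** The point holds as a modest, optional improvement. As written, a valid single-dose pair is left out of the analysis if the Day 8 or Day 35/38 profile is inadequate, if three or more in-clinic doses are missed in either course, or if a deviation affects only steady state or immunogenicity.

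The loss is conditional and the documents do not allow its frequency to be estimated. The range from zero gain to the 28-to-40 ceiling rests on borrowing the steady-state CV of 30% and true ratio of 0.95 for the single-dose ratio. It should not be read as an expected gain of 12 pairs, since the 30% allowance covers every reason for exclusion. Neither the primary equivalence test nor any formal decision is affected. The case for acting is that SAP 6.5.2 draws a conclusion from these intervals and the data needed to support it better are already collected.

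**What to change.** Define a single-dose PK set in SAP 3.2, and refer to it in SAP 6.5 and 6.5.2. It would contain Group 1A and 2A participants with:

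- two AV7909 doses per protocol;
- evaluable AUC0-12h and Cmax on both single-dose days (4 and 31, or 2 and 32);
- no deviation affecting those two profiles.

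The SAP 6.4 pre-dose rule continues to apply. Keep the present PK Population for the primary analysis.

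Protocol 10.3 names four populations and assigns the PK Population to every PK analysis. Record the new set in the SAP as a change from that section, or align the section at the next amendment, so that the two documents do not conflict.

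The cost is a paragraph in SAP 3.2, two cross-references and the record of the change, all before database lock. No new data are needed. The downside is that denominators may differ between the primary and secondary PK tables; a footnote giving the number in each set deals with that.

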### 3.3 Multicenter Study

This study is expected to enroll 210 participants at approximately 4 sites in the United States. Subject randomization and protocol deviations will be summarized by site and treatment group.

### 3.4 Analysis Time Points

Participant visits occur on protocol-specified days with associated visit windows. The schedule may shift by  $\pm 1$  day at the following visits:

- Day 23 visit of the second vaccination for all participants.
- Day 37 visit of TNA assessment for Group 1, 2B, and 3. There is no shifting flexibility for Group 2A at this visit as PK assessment schedule at Day 38.
- Day 51 of final study visit for all participants.

If not otherwise specified, for the purposes of analysis, the analysis visits will be assigned as provided in **Table 2** for vaccination, immunogenicity (TNA) testing, clinical laboratory data,

vital signs, and physical examinations. Data at unscheduled visits will not be presented in the by-visit summary analyses but will be included in the summary tables by maximum toxicity grade or abnormality when applicable, and in data listings.

**Table 2 Analysis Windows for Vaccination, Immunogenicity (TNA) Testing, Clinical Laboratory Data, Vital Signs, and Physical Examinations**

Analysis Visit	Nominal Day	Lower Limit of Study Day	Upper Limit of Study Day
Baseline	NA	-28	Prior to the first exposure to any study treatment
Day 1	1	1	1
Day 8	8	8	8
Day 23	23	22	24
Day 37	37	36 for Group 1, 2B, and 3, 37 for Group 2A	38 for Group 1, 2B, and 3, 37 for Group 2A
Day 51	51	50	52

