3.2.2. Secondary Endpoints

Safety

- Incidence of AEs from the first dose of any IP through the Final Study Visit (Day 51 ± 1 d)
- Incidence of serious AEs (SAEs) from the first dose of any IP until the 12-month follow-up (Day 388 ± 14 d)
- Incidence of solicited systemic and injection site reactions reported in participant e-diaries following each vaccination
- Incidence of AESIs from the first dose of any IP until the 12-month follow-up (Day 388 ± 14 d)
- Incidence of clinical laboratory abnormalities

Pharmacokinetics and Immunogenicity

- AUC_{0-12h} and C_{max} for ciprofloxacin on Days 4 and 31 and for doxycycline on Days 2 and 32
- Geometric mean TNA 50% neutralizing factor (NF_{50}) values 2 weeks after the second vaccination (Day 37 ± 1 d)

AV7909 Anthrax Vaccine

IND 014451

Protocol EBS.AVA.210, Version 3.0 (28 October 2019)

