8.1.2.14. Group 1A: Day 37 (± 1 d) – Blood Draw for TNA

The Day 37 visit to draw blood for immunogenicity may shift by ± 1 d. If such a shift in visit day occurs, the participant must remain on ciprofloxacin 500 mg po every 12 hours until the morning of that visit. In the event of such a shift, the participant's required number of doses of ciprofloxacin will vary. The Pharmacy Manual will contain a table detailing the dosing options for the final course of ciprofloxacin given a one-day shift from Day 37.

1. Participants will report to the clinic having taken their morning dose of ciprofloxacin at home.

AV7909 Anthrax Vaccine

IND 014451

Protocol EBS.AVA.210, Version 3.0 (28 October 2019)

2. Review participant's ciprofloxacin supply; count the number of remaining doses and compare to the e-diary record to document compliance; record total remaining in source document and eCRF.
3. Review other e-diary entries with participant. Discuss any changes in the use of concomitant medication as well as any vaccination reactions if still ongoing. Remind participants that they should still use sunscreen and avoid excessive sun exposure and strenuous sports until the Day 51 Final Study Visit.
4. Record concomitant medications.
5. Collect blood sample for TNA assessment.

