For the abbreviations used above please refer to [Table 1](#) of the protocol. *The \pm 1 d window applies only to the second vaccination on Day 23 (note: the second course of antibiotic treatment will have to shift accordingly). [†]At Home Days are only those days where both doses of doxycycline are taken at home. [§]The +1 d window only applies to Day 31. [‡]For EWV occurring within the visit window of Day 37, a blood sample for TNA will be drawn.

^a PM and AM admissions must be timed so that doxycycline can be administered in the clinic within a 12 hr \pm 30 min window of the prior AM or PM dose.

^b For each PK session, the sites will manage the meals and activity of participants as detailed in [Protocol Section 5.3.1](#) and [Protocol Section 5.3.2](#).

^c Eligibility will be reviewed before each vaccination, either the evening before (ie, on Day 7) or the morning of vaccination (ie, on Day 23).

^d Physical examinations (PE) will be conducted as described in [Protocol Section 8.3.3](#).

^e ECGs will be conducted and interpreted at screening as described in [Protocol Section 8.3.3](#).

^f Vital signs will be administered as described in [Protocol Section 8.3.4](#).

^g Pregnancy tests (serum and/or urine) will be administered to all WOCBP as described in [Protocol Section 8.3.2](#). Serum pregnancy test will be performed at Screening visit for WOCBP, while urine pregnancy tests for WOCBP required before each vaccination will be performed either the evening before (ie, on Day 7) or the morning of vaccination (ie, on Day 23). Note: for WOCBP in group 2A, UPT is required only at Day 7 (at the evening admission); it is not required at evening admissions at Day 1, 31 or 37. FSH test will be performed at Screening visit only for postmenopausal women.

AV7909 Anthrax Vaccine

IND 014451

Protocol EBS.AVA.210, Version 3.0 (28 October 2019)

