8.1.4.11. Group 2A: Day 37 – Blood Draw for TNA

1. Collect doxycycline supply, review e-diary dosing entries to confirm compliance with doxycycline dosing to document compliance, discuss changes in the use of concomitant medications, as well as any vaccination reactions, if still ongoing, and remind participants about the dietary and activity precautions that must be followed when taking doxycycline (see [Section 5.3](#)).
2. Collect blood sample for determination of doxycycline trough concentrations prior to the in-clinic administration of the AM dose of doxycycline [100 mg po 12 hours after evening dose (± 30 min)]; record time of administration of doxycycline in source document and eCRF.
3. Following doxycycline dose administration, collect blood sample for TNA assessment.
4. Prior to discharge on the morning of Day 37, return doxycycline supply and remind participants to return to clinic that evening for the fourth overnight admission.

8.1.4.12. Group 2A: Day 37 – Evening & Overnight Stay # 4

1. Admit to clinic for overnight stay #4.
2. Staff will review the participant's doxycycline supply and review e-diary entries with participant, checking doxycycline dosing records to document compliance, discuss if they required the use of concomitant medications, as well as any vaccination reactions if still ongoing and will remind participants about the diet and activity precautions that must be followed when taking doxycycline (see [Section 5.3](#)).
3. Administer doxycycline 100 mg po 12 hours after morning dose (± 30 min); record time of administration of doxycycline in source document and eCRF.

AV7909 Anthrax Vaccine

IND 014451

Protocol EBS.AVA.210, Version 3.0 (28 October 2019)

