8.2. Immunogenicity/Efficacy Assessments

For all participants, blood samples for the determination of TNA titers will be collected on Day 1 and Day 37 (± 1 d) (2 weeks after the last vaccination). Blood samples will be collected at the EWV only if it falls within the visit window for Day 37.

All immunogenicity laboratory samples will be evaluated using a TNA assay. Specific procedures related to collection, processing, storage, and shipment of the samples will be provided in a Laboratory Manual.

The TNA assay being used in this trial has been validated by Battelle Memorial Institute (Columbus, Ohio) under National Institute of Allergy and Infectious Diseases sponsorship. The assay measures the functional ability of antisera containing anti-PA antibodies to specifically protect cells against *B. anthracis* lethal toxin cytotoxicity {[Stinson et al, 2005](#); [Li et al., 2008](#)}. The TNA assay results will be reported as the reciprocal of a serum sample dilution that results in 50% neutralization of lethal toxin cytotoxicity (50% effective dilution; ED₅₀). To standardize assay results, the results are divided by the ED₅₀ of a serum reference standard, and the resulting ratio is reported as a 50% neutralization factor, NF₅₀. Reference standard AVR801 will be used.

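### SAP Table 2 accepts a Group 2A TNA sample only on study Day 37, although the endpoint is Day 37 ± 1 day and a permitted schedule shift can put the draw on Day 38

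*SAP*

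**What the plan says.** **Endpoint and general statements.** Protocol 3.2.2 defines the secondary endpoint as geometric mean TNA NF50 "values 2 weeks after the second vaccination (Day 37" ± 1 d). Protocol 8.2 says of all participants that "blood samples for the determination of TNA titers will be collected on Day 1 and Day 37" (± 1 d). SAP 2.2.3 repeats Day 37 (± 1 day) for all participants. None of the three excepts Group 2A.

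**Analysis windows.** SAP 3.4 lists among the permitted ± 1 day shifts the "Day 37 visit of TNA assessment for Group 1, 2B, and 3", and then excludes Group 2A: "There is no shifting flexibility for Group 2A at this visit as PK assessment schedule at Day 38". Table 2 sets Days 36 to 38 for Groups 1, 2B and 3, and Day 37 to Day 37 for Group 2A. SAP 3.2 makes a Day 37 result inside the window a condition of entry to the Immunogenicity Population. SAP 4.3 counts study days from randomization.

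**Group 2A visit schedule.** Protocol 8.1.4.11 is headed "Group 2A: Day 37 – Blood Draw for TNA", with no window, and the TNA window cell in Table 7 is empty. At that visit staff "remind participants to return to clinic that evening for the fourth overnight admission", and the steady-state PK session follows on Day 38. The Table 7 footnote says that the + "1 d window only applies to Day 31", and 8.1.4.8 is headed with the same +1 d. Vaccination 2 may fall on Day 23 ± 1 (8.1.4.7), and at discharge from it participants are told to come back eight days later.

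**The concern.** The analysis window for one subgroup is narrower than the endpoint as defined, and the reason given for it holds only on the unshifted calendar. If a Group 2A participant uses shifts that the protocol allows, the final PK session need not be on Day 38. A sample taken exactly two weeks after vaccination 2 could then be set aside, while a Day 38 sample from Groups 1, 2B or 3 is kept. Only the Group 2 versus Group 3 non-inferiority comparison is exposed. At stake are some evaluable doxycycline participants and an inclusion rule that differs between participants contributing to the same comparison.

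**Working it through.** **1. Windows side by side**

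| Group | Protocol visit section | SAP Table 2 |
|---|---|---|
| 1A | ± 1 d (8.1.2.14) | 36–38 |
| 1B | ± 1 d (8.1.3.6) | 36–38 |
| 2A | none given (8.1.4.11, Table 7) | 37 only |
| 2B | ± 1 d (8.1.5.6) | 36–38 |
| 3 | ± 1 d (8.1.6.3) | 36–38 |
| All (protocol 3.2.2 and 8.2; SAP 2.2.3) | ± 1 d | – |

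Table 2 agrees with the visit section in each group. It disagrees with the endpoint and the general TNA statements in Group 2A.

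**2. Following the Group 2A calendar**

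| Step | Rule | On schedule | Shifted |
|---|---|---|---|
| Vaccination 2 | Day 23 ± 1 (8.1.4.7) | 23 | 24 |
| Third overnight admission | 8 days later (8.1.4.7); Day 31 + 1 d (8.1.4.8) | 31 | 32 |
| Single-dose PK | next day (8.1.4.9) | 32 | 33 |
| TNA draw | 37 − 31 = 6 days after admission | 37 | 38 |
| Steady-state PK | day after the TNA visit | 38 | 39 |
| Vaccination 2 to draw | difference | 14 d | 14 d |
| Table 2, Group 2A | 37 only | in | out |
| Table 2, other groups | 36–38 | in | in |

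The shifted column assumes that the spacing between visits is kept. Protocol 4.3.3 supports that, because it plans seven days of doxycycline before steady state is tested, but no section states it for Group 2A. If the draw stayed on study Day 37 instead, it would be inside Table 2, at 37 − 24 = 13 days after vaccination 2.

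The Table 2 windows alone (vaccination 2 on Days 22–24, TNA on Days 36–38) admit intervals from 36 − 24 = 12 to 38 − 22 = 16 days in the other groups. The excluded Group 2A sample, at 14 days, lies in the middle of that range.

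**3. Size**

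The plan's figure is 53 evaluable per group: true ratio 0.85, margin 0.5, CV 100%, one-sided 2.5%, 90% power (protocol 10.2, SAP 2.4).

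- Log SD = √ln(1 + 1²) = √0.6931 = 0.8326
- Distance from the margin = ln(0.85/0.5) = 0.5306
- Normal approximation: n = 2 × (1.960 + 1.282)² × 0.6931 / 0.5306² = 51.7, so 52
- Noncentral t: n = 53 gives power 0.902, and n = 52 gives 0.896. The figure reproduces.
- Allowance: 70 × 0.75 = 52.5, so about 70 − 53 = 17 losses per group are covered.

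The documents give no rate of shifting, so the losses below are assumed. They come from Group 2 only, with Group 3 held at its starting size.

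| Lost from Group 2 | Power from 70 per group |
|---|---|
| 0 | 0.963 |
| 4 | 0.958 |
| 8 | 0.952 |
| 10 | 0.949 |
| 17 | 0.935 |

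If the 25% allowance is already used up (53 per group, with about 40 × 0.75 = 30 of Group 2's 53 in Group 2A), losing 2, 3, 6 or 15 more gives 0.896, 0.893, 0.883 or 0.843.

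**The case against.** The strongest reply is that the SAP copies the protocol's own Group 2A schedule. The visit heading and Table 7 carry no window for Group 2A, while each other group's section does; for Group 1A, for example, "The Day 37 visit to draw blood for immunogenicity may shift by" ± 1 d. On that schedule a Group 2A draw on Day 36 or 38 is off plan, and the SAP gives a reason, the PK session due on Day 38. No section says outright that the draw moves when the Day 31 admission does. The only forward-shift text is in the Group 1A footnote to Table 5, which says Day 37 may not need to move because it has a window. A shifted Group 2A participant would also be in clinic on the morning of study Day 37 for a trough, so a draw that day is feasible.

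Much of this stands. A reader might infer that the SAP discards samples the protocol plainly treats as valid. The documents do not support that, because the protocol's general statements and its Group 2A schedule point different ways. A reader might also infer that a whole arm is under a stricter rule. It is not: Group 2A is a subgroup, and Group 2B, in the same doxycycline arm, has ± 1 day.

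The reply does not dispose of the point. The Day 38 PK reason lapses once the session moves to Day 39. The Group 1A footnote relies on a Day 37 window that Group 2A lacks. The site instruction also places the TNA draw at the visit before the final PK session, and nothing tells sites to detach it.

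**Conclusion.** The inconsistency is real and modest. Table 2 is narrower than the stated endpoint for Group 2A, and the protocol leaves open a route by which a draw 14 days after vaccination 2 lands outside it. Two assumptions carry this: that the later Group 2A visits move in sequence with the admission, and that the window required by SAP 3.2 is the one in Table 2.

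The number affected is unknown. The ceiling is the roughly 40 of 70 (57%) in Group 2A, but that is the share of Group 2 in the subgroup, not the share expected to shift. A material loss of power should not be inferred: losses up to 17 fit within the planned allowance if few other exclusions occur, and power then stays at 0.935 or above. These power figures treat the losses as unrelated to response, and nothing in the documents points to a bias. The case for changing the window is consistency with the endpoint and keeping correctly timed samples.

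**What to change.** Before database lock:

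1. In SAP Table 2, set the Day 37 TNA analysis window to Days 36–38 for all groups, and remove the Group 2A exception from SAP 3.4.
2. Add the Group 2A Day 31 (+1 d) shift to the permitted shifts in SAP 3.4.
3. Reconcile the unwindowed Group 2A wording (protocol 8.1.4.11 and Table 7) with the ± 1 day statements in protocol 3.2.2 and 8.2 and SAP 2.2.3, and state whether the TNA draw moves when the Day 31 admission does. Widening Table 2 without this step would leave the SAP at odds with the Group 2A visit schedule.

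The cost is wording: no new data and no change to the planned 53 evaluable or 70 randomized per group. The small downside is that Group 2A samples taken one day off the nominal visit would be analysed, as they already are in every other group.
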